Complete Title: Evaluating a Marketing Campaign to Increase Participation in School Meals

Short Title: Increasing School Meal Participation

Protocol Date: July 19, 2024

NCT #: NCT06419218

Study Principal Investigator:

[name]
Stanford University
email: [contact]

Introduction

The goal of these analyses is to examine whether parental exposure to a social media campaign encouraging school meal participation increases the frequency with which children eat school lunch and school breakfast. This analysis plan pre-specifies the analyses before collecting data and therefore serves as our ex-ante planned analysis.

Study Protocol

Participants will complete a randomized controlled trial. After providing informed consent, participants will take a baseline survey programmed in Qualtrics. At the end of the survey, participants will be randomized to 1 of 2 arms: 1) school meal campaign or 2) control campaign (focused on reading, a neutral topic unrelated to school meals). In the school meal campaign arm, participants will be asked to join a private Facebook group where they will view messages about the benefits of children eating school meals. In the control arm, participants will be asked to join a private Facebook group where they will view messages about the benefits of their children reading (a neutral topic unrelated to school meals). In both arms, researchers will post messages to the private Facebook groups approximately twice per week for 6 weeks. After the 6-week campaigns end, participants in both arms will take a follow-up survey programmed in Qualtrics.

Statistical Considerations

General Principles

Primary analyses will be intent-to-treat, including all randomized participants regardless of whether they joined a Facebook group or completed the follow-up survey. Depending on the proportion of participants who join the Facebook groups, we may consider conducting secondary, per-protocol analyses including only participants who joined a Facebook group.

We will use a two-sided critical alpha of 0.05 to conduct all statistical tests. All confidence intervals presented will be 95% and two-sided.

Outcome Measures

Table 1 describes the outcome measures.

Table 1. Outcome measures

Outcome	Description	Timing of Assessment
Co-primary outcomes		

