Barriers to children's school lunch consumption	Parental report of the barriers preventing their child from eating school lunch. Assessed with 1 item: "What are some reasons that your child doesn't eat school lunch more often? Check all of the reasons that apply."	Collected in a ~10 minute survey at baseline and again at 6 weeks.
	Response options list 15 reasons plus "NA - my child eats school lunch every day or almost every day" and a free response option for "other." Total number of barriers selected will be summed. Those who report "NA - my child eats school lunch every day or almost every day" will be coded as having 0 barriers.	

Outcome	Description	Timing of Assessment
Barriers to children's school breakfast consumption	
Parental report of the barriers preventing their child from eating school breakfast. Assessed with 1 item: "What are some reasons that your child doesn't eat school breakfast more often? Check all of the reasons that apply." Response options list 16 reasons plus "NA - my child eats school breakfast every day or almost every day" and a free response option for "other." Total number of barriers selected will be summed. Those who report "NA - my child eats school breakfast every day or almost every day" will be coded as having 0 barriers.
	Collected in a ~10 minute survey at baseline and again at 6 weeks.
Food insecurity	
Household food insecurity
 
Parental report of household food insecurity. Assessed with 6 items (e.g., "In the last month, were you ever hungry but didn't eat because there wasn't enough money for food?") Response options include "no" or "yes"; "never true", "sometimes true", or "often true"; "only 1 or 2 days," "some days but not every day," or "almost every day." Responses of "often" or "sometimes" and "yes" are coded as affirmative (yes). Likewise, responses of "almost every day" and "some days but not every day" are coded as affirmative (yes). The sum of affirmative responses to the six questions in the module is the household's raw score on the scale.
 
Household food security status is assigned as follows:
 
Raw score 0-1—High or marginal food security
 
Raw score 2-4—Low food security
 
Raw score 5-6—Very low food security
 
Analyses will dichotomize households into those with high or marginal food security and those with low or very low food security.
	Collected in a ~10 minute survey at baseline and again at 6 weeks.

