Outcome	Description	Timing of Assessment
Child food insecurity	
Parental report of child food insecurity. Assessed with 8 items (e.g., “In the last month, did you ever cut the size of your child's meals because there wasn't enough money for food?”) Response options include “no” or “yes”; “never true”, “sometimes true”, or “often true”; “only 1 or 2 days,” “some days but not every day,” or “almost every day.” Responses of “often” or “sometimes” and “yes” are coded as affirmative (yes). Responses of “almost every day” and “some days but not every day” are coded as affirmative (yes). The sum of affirmative responses to the 8 questions in the module is the child's raw score on the scale.
 
Child food security status is assigned as follows:
 
Raw score 0-1—High or marginal food security among children
 
Raw score 2-4—Low food security among children
 
Raw score 5-8—Very low food security among children
 
Analyses will dichotomize households into those with children with high or marginal food security and those with children with low or very low food security.
	Collected in a ~10 minute survey at baseline and again at 6 weeks.

Data Preparation

To prepare the data, we will examine all scales to ensure they achieve adequate internal consistency (Cronbach's $\alpha > 0.70$), dropping items as needed to improve internal consistency. If we are unable to achieve adequate internal consistency by dropping items, we may exclude the unreliable scales from analyses (e.g., not analyze treatment effects on these outcomes).

Statistical Methods

1. Analyses of the co-primary outcomes:

- a. We will use mixed effects regression models to **evaluate the effect of the school meals campaign on children's school lunch consumption and children's school breakfast consumption**. In separate models for lunch and breakfast, we will regress usual number of school meals eaten per week on an indicator variable for trial arm (school meal campaign vs. control), an indicator variable for time period (baseline vs. follow-up) and the interaction between trial arm and time period. The treatment effect is given by the coefficient on the interaction term. We will consider linear or Poisson models, based on the distribution of the outcome and model fit. We will treat the intercept as random to account for repeated measures within participants and will include state fixed effects.

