- b. To **examine the potential differential effects of the school meals campaign by demographic characteristics**, analyses will examine whether the effect of the school meals campaign on children's school lunch consumption and children's school breakfast consumption is modified by household income (\leq vs. $>185\%$ Federal Poverty Level) or parent's race/ethnicity (with categories determined based on distribution of race/ethnicity in the sample). We will test for effect modification by adding to the primary model three-way interactions (i.e., difference-in-difference-in-differences) between trial arm, time period, and variable(s) for the potential effect modifier, using separate models for each outcome (school lunch consumption and school breakfast consumption) and effect modifier (income and race/ethnicity).

2. Analyses of the secondary outcomes:

- a. We will use a similar mixed effects regression approach to **evaluate the effect of the school meals campaign on secondary outcomes** (e.g., perceived benefits of school meals, knowledge and attitude about school meals, behavioral intentions, perceived barriers to school meal participation, and food insecurity). We will use mixed effects logistic regression for binary outcomes, mixed effects linear regression for continuous outcomes, and mixed effects Poisson regression for count outcomes. We will treat the intercept as random to account for repeated measures within participants. For outcomes measured only at follow-up (e.g., noticing), we will use linear, logistic, or Poisson regression.

Sample Size Needs

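### Both food-insecurity outcomes are analysed only as a split at raw score 2, so movement between low and very low does not show and very low is never identified

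*Combined protocol and SAP*

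**What the plan says.** Outcome Measures, Table 1, lists household food insecurity (6 items) and child food insecurity (8 items) as secondary outcomes, each measured at baseline and 6 weeks. Both rows first build a sum. For children, "The sum of affirmative responses to the 8 questions in the module is the child's raw score on the scale". Both then assign three levels. Scores 0-1 are high/marginal. The next child level is "Raw score 2-4—Low food security among children" and the last is "Raw score 5-8—Very low food security among children". The household scale uses the same lower cut-offs and ends at "Raw score 5-6—Very low food security".

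Both rows close by collapsing the three levels to two: for the household scale "Analyses will dichotomize households into those with high or marginal food security and those with low or very low food security", for the child scale "Analyses will dichotomize households into those with children with high or marginal food security and those with children with low or very low food security". Statistical Methods, item 2a, names food insecurity among the secondary outcomes and sets the model by outcome type: "We will use mixed effects logistic regression for binary outcomes, mixed effects linear regression for continuous outcomes". It also provides mixed Poisson models for counts. No section analyses either raw score, the three-level status, or very low on its own.

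**The concern.** The plan defines its most severe level and then does not use it. A child whose score rises from 2 to 8 counts as unchanged, and so does one who improves from 8 to 2, while a move from 1 to 2 counts as a full change. If the campaign alters severity among families who are already food insecure, the planned model can miss it, and a null on the dichotomy could be read as no effect on food insecurity. The split also discards information that the trial collects and scores anyway. The other summed outcomes in Table 1 (topics recognized, and barriers to lunch and breakfast) keep their totals; only the two food-insecurity sums are cut to 0/1. A severity analysis added after the results are known would not have pre-specified standing.

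**Working it through.** **1. The plan's own power figure.** Sample Size Needs gives f = 0.05, n = 600, correlation 0.60, alpha 0.05 and 80% power for the co-primary outcomes. For a 2 × 2 within-between interaction, λ = f² × N × 2/(1 − ρ) = 0.0025 × 600 × 2/0.4 = 7.5. The noncentral F(1, 598) then gives 78.1%, so the figure reproduces to within 2 points. This point does not depend on it; the plan states no power for food insecurity.

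**2. Which moves the binary registers.** This follows from the cut-offs in Table 1 and needs no assumption. Counts are pairs of raw scores, in each direction.

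| Move | Child (0-8) | Household (0-6) | Binary changes? |
|---|---|---|---|
| low ↔ very low | 3 × 4 = 12 | 3 × 2 = 6 | none |
| high/marginal ↔ very low | 2 × 4 = 8 | 2 × 2 = 4 | all |

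Moves in the second row are counted, but they look the same as moves between high/marginal and low. As an invented illustration, control at 70/22/8% and campaign at 70/26/4% across the three levels both give 30% on the binary, a difference of zero, although very low has halved.

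**3. Information kept by the split.** The documents give no prevalence or effect size here, so these inputs are assumptions:
- 300 completers per arm (600/2; the allocation ratio is not stated, 1:1 assumed);
- probability of an affirmative answer to item j = 1/(1 + exp(−2(θ − b_j))), with b_j evenly spaced from −2 to 2.5;
- θ with SD 1.5, correlation 0.8 over time, and mean −2.5, −1.5 or −0.5, which puts baseline low/very low in the child module at 25-72%;
- a latent shift of 0.3 (d = 0.3/1.5 = 0.20) or 0.15 (d = 0.10);
- a z-test on change scores at two-sided 0.05, 1,500 runs per setting.

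Relative efficiency = (mean z of split / mean z of raw score)². At the shift of 0.3, for the three latent means in order:
- 8 items: 0.55, 0.51, 0.40
- 6 items: 0.50, 0.53, 0.46

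The loss is similar at half the shift.

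| Module | Latent d | Power, split | Power, raw score |
|---|---|---|---|
| Child | 0.20 | 34-46% | 56-79% |
| Child | 0.10 | 13-16% | 19-29% |
| Household | 0.20 | 28-41% | 49-71% |
| Household | 0.10 | 11-15% | 17-28% |

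Simulation error is about √(0.5 × 0.5/1,500) = 1.3 points at most per setting, and repeat runs moved the ends of these ranges by up to about 3 points.

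**4. Very low as its own endpoint.** Take an assumed control rate of 8%, halved to 4%, with 300 per arm at follow-up:
- null SE = √(2 × 0.06 × 0.94/300) = 0.01939
- alternative SE = √((0.08 × 0.92 + 0.04 × 0.96)/300) = 0.01932
- power = Φ((0.04 − 1.96 × 0.01939)/0.01932) = Φ(0.103) = 54%

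Other assumed control rates, each halved: 2% gives 17%, 4% gives 30%, 10% gives 64%, 15% gives 83%. A separate result for very low would be descriptive unless the rate were near 15%.

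**The case against.** The dichotomy is pre-specified, is applied the same way to both scales, and contradicts nothing else in the plan. These are secondary outcomes without stated power. The raw score and the three levels are derived at both time points, so nothing is lost at measurement. All of that stands, and it is why this is a matter of analysis wording and not of design.

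The simulated gain can be called flattering. A latent d of 0.20 is twice the 0.10 stated in Sample Size Needs, and food insecurity is more distal than meal consumption. At 0.10 neither analysis is well powered. At lower prevalence power also falls: with d = 0.20, about 19% (split) against 36% (raw score) near 10% prevalence, and 14% against 25% near 5%. The z-test on change scores is not the planned mixed logistic model. These limits stand. One qualification: the plan's power figure reproduces at a difference in change of 0.20 SD, since 0.20/(√0.8 × √(2/300)) = 2.74 = √7.5, so both rows are shown and the conclusion rests on neither alone.

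Extra models also add tests, since the plan says "We will use a two-sided critical alpha of 0.05 to conduct all statistical tests" and describes no multiplicity adjustment. Labelling the addition supportive answers this.

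Two stronger readings are tempting, and the documents do not support them. A reader might infer that the outcome cannot register any move into or out of very low. It can: every move between high/marginal and very low changes the binary. A reader might also take food insecurity to be the trial's harm measure. There are two such outcomes, the plan calls neither one a harm or safety measure, and item 2a lists food insecurity among the outcomes on which the campaign's effect is evaluated.

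**Conclusion.** The point holds in limited form. From the text alone, the planned analysis of both modules cannot show movement between low and very low and never identifies very low. A zero effect on the binary follows by construction only if all movement lies between those two levels, which is an extreme case and not an estimate. The size of the information loss rests on the assumed item model: the split keeps roughly 40-55% of what the raw score carries. Using the raw score raises power at either shift, but at d = 0.10 it remains below 30%, so the change makes better use of the data without making these outcomes well powered. The co-primary analyses and the sample size are unaffected. This is an inexpensive improvement to two secondary outcomes.

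**What to change.** Keep the dichotomy as planned. For both modules, add to Statistical Methods, item 2a:

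1. A supportive arm-by-time mixed model on the raw score already computed (0-6 and 0-8), with a random intercept as in the other repeated-measures models and the model family named in advance. Label it supportive, so that it adds no confirmatory test.
2. A descriptive table by arm of the three-level status at baseline and 6 weeks, including the number entering and the number leaving very low, without a significance test.

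The cost is a few lines of plan wording, two more supportive results and one table. No new data are needed.

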Children's consumption of school lunches	Parental report of the usual number of days per week their child ate school lunch during the past month. Assessed with 1 item: "Thinking about the last month, how many days a week did your child usually eat school lunch ?" This item will be scored on a 6-point scale from "0 days per week" (0) to "5 days per week" (5).	Collected in a ~10 minute survey at baseline and again at 6 weeks.
Children's consumption of school breakfasts	Parental report of the usual number of days per week their child ate school breakfast during the past month. Assessed with 1 item: Thinking about the last month, how many days a week did your child usually eat school breakfast ?" This item will be scored on a 6-point scale from "0 days per week" (0) to "5 days per week" (5).	Collected in a ~10 minute survey at baseline and again at 6 weeks.
Secondary outcomes		
Campaign reactions		
Noticing the school meal campaign	Parental report of whether they noticed the school meal campaign. Assessed with 1 item: "In the last 6 weeks, have you seen any messages or advertising on Facebook encouraging children to eat school lunch or school breakfast?" Response options are "yes" (1) and "no" (0).	Collected in a ~10 minute survey at 6 weeks.
Number of school meals campaign topics recognized	Parental report of the number of topics they recognize having seen in messages about school meals. Assessed with 1 item: "Which of these topics did the messages discuss, if any? Check all that apply." Response options list 8 topics plus options for "none of these" and "not sure." Number of topics recognized will be calculated as the sum of all topics that parents indicate they have seen. Those who answer, "none of these" and "not sure" will be coded as recognizing 0 topics. Those who report not noticing the school meal marketing campaign will be coded as recognizing 0 topics.	Collected in a ~10 minute survey at 6 weeks.
Frequency of reading campaign messages	Parental report of the frequency with which they read their assigned campaign messages. Assessed with 1 item: "In the past month, how often did you read these messages?" This item will be scored on a 5 point scale ranging from "Never or less than 1 time per week" (1) to "Every day or more often" (5).	Collected in a ~10 minute survey at 6 weeks.

Outcome	Description	Timing of Assessment

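### If the co-primary model is linear, one common baseline mean, justified by randomising after the baseline survey, would cut the effect variance by about 16% at the plan's correlation with equal wave variances

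*Combined protocol and SAP*

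**What the plan says.** The Study Protocol section places randomisation after baseline data collection: "At the end of the survey, participants will be randomized to 1 of 2 arms". Table 1 gives the timing of both co-primary outcomes as: "Collected in a ~10 minute survey at baseline and again at 6 weeks".

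Statistical Methods 1a fits arm, time period and arm × time, separately for lunch and breakfast, and states: "The treatment effect is given by the coefficient on the interaction term". On covariance it says: "We will treat the intercept as random to account for repeated measures within participants and will include state fixed effects". The family is left open: "We will consider linear or Poisson models, based on the distribution of the outcome and model fit". General Principles makes the primary analysis intent-to-treat, "including all randomized participants regardless of whether they joined a Facebook group or completed the follow-up survey".

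The same structure carries into section 1b ("We will test for effect modification by adding to the primary model three-way interactions") and, for secondary outcomes, into section 2a, which names "mixed effects linear regression for continuous outcomes". Nothing elsewhere in the document constrains the baseline means to be equal or adjusts follow-up for baseline.

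**The concern.** An arm main effect in a two-wave model lets the baseline means differ by arm. Here they cannot differ in expectation, because arm is assigned only after baseline is recorded. Any observed baseline difference is chance, and the interaction coefficient subtracts it in full. The estimate stays unbiased, but the sampling error of two separate baseline means enters its variance.

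What is at stake is precision on both co-primary outcomes, on the linear effect-modification tests, and on the secondary outcomes that have a baseline and would be modelled linearly. I count six of these: perceived benefits, perceived healthfulness and intentions, each for lunch and breakfast. That count is a reading of Table 1, since section 2a does not list which outcomes it treats as continuous.

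**Working it through.** **Inputs.** From Sample Size Needs: 800 randomised, 75% retained (600), correlation ρ = 0.60, f = 0.05, 80% power. From General Principles: two-sided α = 0.05, all randomised participants analysed. Assumed, because the document does not give them: 1:1 allocation (400 per arm, 300 followed up), dropout at random, and the ratio k of follow-up to baseline variance. Variances are in baseline SD².

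**The plan's own figure.** For a within-between interaction with two groups and m = 2 waves, λ = f²·N·m/(1−ρ) = 0.0025 × 600 × 2 / 0.40 = 7.5. On F(1, 598) this gives 78.1% power, within two points of the stated 80%. In this test f = 0.05 means cell effects of ±0.05 SD, hence a difference in change of 4 × 0.05 = 0.20 SD. As a check, the completers' variance of the difference in change is 4 × 0.40/300 = 0.005333, and 0.20²/0.005333 = 7.5. The plan also equates f = 0.05 with d = 0.10, so both effect sizes are shown below.

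**Variance of the effect, k = 1, linear model.**
- Common baseline mean: 2(1−ρ²)/300 = 2 × 0.64/300 = 0.004267.
- Separate baseline means add 2(1−ρ)²/400 = 2 × 0.16/400 = 0.000800, giving 0.005067.
- Reduction: 0.000800/0.005067 = 15.8%. The ratio 0.005067/0.004267 = 1.1875, or about 19% more participants.
- At 60% or 90% retention the reduction is 13% or 18%.

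**Power, k = 1.** Standard errors are √0.005067 = 0.0712 and √0.004267 = 0.0653.
- At 0.20 SD: 80.2% rises to 86.5%.
- At 0.10 SD: 29.0% rises to 33.4%.
- The effect detectable with 80% power, 2.80 × SE, falls from 0.199 to 0.183 SD.

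**Unequal wave variances.** The planned random intercept with one residual variance forces k = 1. When k differs, its large-sample variance was taken as the sandwich variance at the limiting maximum-likelihood values. The comparator has a common baseline mean and an unstructured 2×2 covariance, with variance 2k(1−ρ²)/300. Variance reduction against the planned model:

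| ρ | k = 0.8 | k = 1.0 | k = 1.2 | k = 1.4 |
|---|---|---|---|---|
| 0.5 | 28% | 20% | 15% | 11% |
| 0.6 | 24% | 16% | 10% | 7% |
| 0.7 | 21% | 12% | 6% | 4% |
| 0.8 | 18% | 8% | 3% | 2% |

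At ρ = 0.6, power for 0.20 SD moves from 84.7% to 92.8% (k = 0.8), 75.4% to 79.8% (k = 1.2) and 70.4% to 73.5% (k = 1.4).

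**How much is due to the constraint.** Within unstructured models, separate baseline means add 2(1−ρ√k)²/400, which vanishes when ρ√k = 1. At ρ = 0.8, k = 1.4, ρ√k = 0.947 and the constraint alone saves 0.4%, against 1.7% for both changes together. This is the largest gap in the table.

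**Why the covariance must change too.** If the constraint is added to the planned random intercept, model-based type I error is about 6.2% to 7.2% at k = 1.2 to 1.4. Robust standard errors repair that, but the variance can then exceed the plan's: 1.035 times at ρ = 0.8, k = 1.4.

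**Simulation.** With 16,000 trials per setting and eight state effects of SD 0.3 (assumed), the variance ratio of recommended to planned model at ρ = 0.6 was 0.762, 0.843, 0.903 and 0.933 for k = 0.8, 1.0, 1.2 and 1.4. Type I error of the recommended model was 5.0% to 5.5%. With integer 0 to 5 outcomes piled at both ends or at zero (assumed, ρ about 0.64), the ratios were 0.854 and 0.865, with type I error 5.2% and 5.0%.

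**Effect modification.** For a binary modifier split 50:50 (assumed), ρ = 0.6 and k = 1, the variance of the three-way term is four times that of the main effect. It falls from 0.0203 to 0.0171, and the 80% detectable difference from 0.399 to 0.366 SD.

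**The case against.** The strongest reply is that nothing is wrong. The planned model is standard, fully stated and unbiased, and it delivers about its stated power. That stands: this is an efficiency point.

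A second reply is that the recommendation bundles two changes, and the constraint alone can be worth almost nothing, or do harm if put into the planned covariance structure. This also stands, but it moves the figures little. The two comparisons differ by at most 1.3 percentage points in the table (1.7% against 0.4%), and the harm arises only if the random intercept is kept.

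Third, the gain may never apply. The outcome is a count of 0 to 5 days, Poisson is open, and the document gives no standard deviation at either wave. That limits the claim to linear models and makes its size conditional, but linear is one of the two named families for the co-primaries and is named for continuous secondaries.

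Fourth, linear and non-linear outcomes would then have different model forms, and a partial implementation is less forgiving than the plan, whose own type I error is about 5.3% to 5.5% at k = 1.2 to 1.4. This is a real cost, met by writing out the full specification.

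Finally, the power gain looks best at 0.20 SD. At 0.10 SD neither model is adequately powered, and this change does not alter that.

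**Conclusion.** The point holds as a recommended improvement, not as a correction of an error. If the co-primary models are linear, the plan leaves unused an equality that its own randomisation guarantees. The variance reduction is 15.8% at ρ = 0.60, 75% retention and equal wave variances, and 1.7% to 27.7% across ρ of 0.5 to 0.8 and k of 0.8 to 1.4. The correlation and retention are the plan's; the variance ratio, allocation and dropout mechanism are assumed. The algebra is secure. The benefit in this trial depends on a variance ratio not yet known, and could be close to nil.

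**What to change.** For the co-primary outcomes if linear, and for the six linear secondary outcomes with a baseline, pre-specify a model in all randomised participants with time and arm × time, no arm main effect, and an unstructured 2×2 within-participant covariance in place of the random intercept. Keep the state fixed effects in the co-primary models. In linear effect-modification models, drop arm and arm × modifier; keep modifier, time, time × modifier, arm × time and the three-way term. Retain the planned model as a sensitivity analysis. State that the constraint is not to be combined with a random intercept and common residual variance, with or without robust standard errors.

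With two waves and no state terms, the estimate equals that from regressing follow-up on baseline and arm among completers. The all-participant form is preferred because it matches the intent-to-treat commitment, not because the 200 without follow-up add precision to it.

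The cost is a changed covariance specification in these linear models, one extra sensitivity analysis and no new data, for a gain that may be small. It should be written into the SAP before analysis.

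### The zero-coded topic count needs robust standard errors named in 2a, because default Poisson intervals would usually be too narrow; as a minor point, 1a leaves the co-primary effect scale open

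*Combined protocol and SAP*

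**What the plan says.** **Topic count.** In Table 1 the item on school meals campaign topics is collected only at 6 weeks. "Response options list 8 topics plus options for" none and unsure, and both of those answers score 0. In addition, "Those who report not noticing the school meal marketing campaign will be coded as recognizing 0 topics". Statistical Methods 2a assigns count outcomes to mixed effects Poisson regression, then adds: "For outcomes measured only at follow-up (e.g., noticing), we will use linear, logistic, or Poisson regression". Neither sentence names a variance estimator, and the plan nowhere mentions overdispersion or robust standard errors. General Principles states: "All confidence intervals presented will be 95% and two-sided".

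**Co-primary outcomes.** In 1a, with separate models for lunch and breakfast, "we will regress usual number of school meals eaten per week" on arm, time period and their interaction. "The treatment effect is given by the coefficient on the interaction term". On the model family: "We will consider linear or Poisson models, based on the distribution of the outcome and model fit". Section 1b adds three-way interactions with income and race/ethnicity to that primary model. The Introduction says: "This analysis plan pre-specifies the analyses before collecting data and therefore serves as our ex-ante planned analysis".

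**The concern.** A Poisson model assumes that the variance equals the mean. Setting every non-noticer to 0 adds a block of zeros to a count that can otherwise reach 8, which usually pushes the variance above the mean. The outcome is measured once per parent, so a random intercept for repeated measures cannot absorb the excess. Default standard errors would then be too small. The intervals would not deliver the promised 95% and, where the arms hardly differ, a significant result could be spurious.

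The smaller issue is pre-specification. The treatment effect in 1a is an interaction coefficient: a difference in days if the model is linear, a log ratio if it is Poisson. The plan names two considerations for choosing between them but no rule. The effect measure for each co-primary outcome, and the scale of the 1b interactions, would therefore be settled after the data are seen.

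**Working it through.** **Inputs.** From Sample Size Needs: 800 parents, 75% follow-up, so 600 analysed; f = 0.05; correlation 0.60. Equal allocation is assumed, giving 300 per arm. From Table 1: 8 topics, non-noticers coded 0. The documents give no noticing rate p and no chance q that a noticer ticks a given topic, so both are assumed: p of 30–90% (campaign) v 10–50% (control), q of 0.3–0.5, ticks independent unless stated.

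**1. The plan's own figure.** For a repeated-measures interaction F test, λ = N·f²·2/(1−ρ) = 600 × 0.0025 × 2/0.40 = 7.5. With 1 and 598 degrees of freedom the power is 78%, close to the stated 80%. The sample size thus appears to rest on a linear-model test.

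**2. Dispersion of the topic count.** Let the count be (noticed: yes or no) × Binomial(8, q).
- Mean = 8pq.
- Mean of the square = p[8q(1−q) + 64q²].
- Variance/mean = (1−q) + 8q − 8pq = 1 + q(7 − 8p).

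This exceeds 1 when p < 7/8 = 87.5%.

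**3. Effect on the interval.** Write φ for variance/mean, μ for the mean, and T and C for the campaign and control arms. For the log ratio of means, the default variance is (1/μT + 1/μC)/300 and the true variance is (φT/μT + φC/μC)/300. The square root of true over default is the factor w by which a correct interval is wider. Default coverage is about 2Φ(1.96/w) − 1.

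Worked case, 70% v 30%, q = 0.4:
- μ = 2.24 and 0.96; φ = 1.56 and 2.84.
- 1/μ sums to 0.446 + 1.042 = 1.488; φ/μ sums to 0.696 + 2.958 = 3.655.
- w = √(3.655/1.488) = 1.57; coverage 79%.

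| Noticing | q | φ (campaign / control) | w | Coverage of default 95% CI |
|---|---|---|---|---|
| 30% v 10% | 0.5 | 3.30 / 4.10 | 1.97 | 68% |
| 70% v 30% | 0.4 | 1.56 / 2.84 | 1.57 | 79% |
| 90% v 50% | 0.3 | 0.94 / 1.90 | 1.25 | 88% |
| 30% v 30% | 0.5 | 3.30 / 3.30 | 1.82 | 72% |
| 50% v 50% | 0.3 | 1.90 / 1.90 | 1.38 | 84% |
| 90% v 90% | 0.4 | 0.92 / 0.92 | 0.96 | 96% |

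Simulation with 300 per arm agrees: 68–89% across the unequal pairs, and about 95% with robust standard errors in every case. If a parent's ticks are correlated (assumed intraclass correlation 0.2), default coverage falls to 64–78%, and to 85–88% even at 90% noticing in both arms.

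**4. Effect on significance.** In the 70% v 30% case the log ratio is ln(0.7/0.3) = 0.847. The default standard error is √(1.488/300) = 0.070 and the true one √(3.655/300) = 0.110, so z is about 12 or 7.7 and the conclusion is the same. With equal noticing of 30–50% there is no effect, and the false-positive rate is one minus coverage: about 16–28% instead of 5%.

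**5. Scale of the co-primary effect.** A gain of 0.3 days is a ratio of 1.8/1.5 = 1.20 from a mean of 1.5 days but 3.8/3.5 = 1.09 from 3.5 days. For interactions even the sign can change. In a constructed example, one subgroup gains 0.4 days from 2.0 and another 0.25 from 1.0. The contrast is +0.15 days, but ln(2.4/2.0) − ln(1.25/1.0) = −0.041 on the log scale.

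In simulations of assumed 0–5 distributions (400 per arm, 75% follow-up, correlation 0.60, state effects omitted), the null rejection rate was 4.7–6.0% even when the smaller of the linear and Poisson p-values was always taken.

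**The case against.** **On the topic count.** Section 2a does not expressly assign this outcome to Poisson, and it also lists linear regression, which kept 94–96% coverage in the scenarios tried. Silence about standard errors is not a commitment to the default. The outcome is secondary, and the noticing and ticking rates are assumed. With independent ticks and unequal noticing, default and robust tests disagreed on significance in about 2% of simulated trials or fewer. All of this stands, and it makes the point conditional and confines the harm mostly to the interval. It does not remove the point: the plan sends counts to Poisson, promises 95% intervals and does not say how they will be obtained. Noticing above 87.5% is unlikely in a control arm that is shown messages about reading.

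**On the co-primary outcomes.** Choosing between linear and Poisson on distribution and fit is common practice, each test is valid on its own scale, and nothing pools lunch with breakfast. The interaction example is small: with an SD of 1.9 days and equal subgroups (both assumed), the standard error of such a contrast is about 0.28 days. These points stand, which is why this part is minor.

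**Stronger readings that a reader might infer.**
- *The two considerations in 1a conflict, because counts must go to Poisson.* That rule stands in 2a, for secondary outcomes. Section 1a has its own sentence, and a 0–5 outcome heaped at 5 would point to linear on both distribution and fit.
- *The choice of model could readily reverse the primary result.* The sharpest disagreements arise against a Poisson model that fits frequent lunch-eating badly, which the plan's own fit criterion would reject.
- *The co-primary intervals would also be too narrow.* In the simulated 0–5 outcomes, default Poisson standard errors were too large, at 1.07–1.64 times the true value.

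**Conclusion.** The main point holds conditionally. If topics recognised is fitted by Poisson regression with default standard errors, its nominal 95% intervals will usually be too narrow. Correct intervals are 1.25–1.97 times as wide over the unequal noticing pairs considered. False positives become a concern only when the arms differ little in noticing. The figures rest on assumed p and q, 300 completers per arm and, unless stated, independent ticks. The 87.5% threshold depends only on the 8-topic scale, the zero coding and independence. With correlated ticks the problem is worse. It is absent where noticing is very high in both arms and ticks are independent.

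The co-primary point is a gap in pre-specification of the effect measure and the interaction scale. It is not a validity problem, and the coverage figures for the topic count lend it no weight.

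**What to change.** **In 2a, add:** *Number of topics recognised will be analysed by Poisson regression with robust (sandwich) standard errors.* This is one sentence and a software option. The cost is wider intervals for this secondary outcome.

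**In 1a, replace the sentence on model choice with:** *Both co-primary outcomes will be analysed with a linear mixed model, with the effect reported as a difference in days per week; a Poisson mixed model is a sensitivity analysis.* Linear matches the F-test power calculation in Sample Size Needs. Naming Poisson for both would not be an equivalent cure: in lunch-like distributions with assumed means of 3.1 and 3.9 days, its null rejection rate was 1.0% and 0.1%, so it would be severely conservative. The team gives up choosing the family after seeing the data, and a breakfast outcome with many zeros is reported in days rather than as a ratio. Naming the model does not remove the scale dependence of interactions; it fixes the scale in advance. Neither change needs new data.
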